9 PHARMACOKINETICS AND PHARMACODYNAMICS

9.1 Pharmacokinetics

Pharmacokinetic variables will be analyzed for all participants in the PK-PPS. Bimekizumab plasma concentrations will be summarized for each treatment at each scheduled visit.

PK summaries will be based on observed values. No imputation will be used. However, if plasma concentration measurements are below the level of quantification (BLQ), then for calculation of the derived statistics the result will be set to ½ of the lower level of quantification (LLOQ). Descriptive statistics including geometric mean, geometric coefficient of variation, and geometric mean 95% CI if applicable will be calculated if at least 2/3 of the values of interest are above the LLOQ. If this is not the case, only median, minimum, and maximum will be presented.

Geometric mean plasma concentration will be plotted by treatment group, and by cumulative antibody status for participants randomized to bimekizumab on linear and log linear scale. In addition, HiSCR₅₀ response (0=not achieved, 1=achieved) assessed at each PK visit (excluding Week 1) will be plotted against the visit's bimekizumab plasma concentration, separated by treatment group. Spaghetti plots of bimekizumab plasma concentrations by week from bimekizumab first dosing separated by treatment group and antibody status will be presented for participants with and without HiSCR₅₀ response at Week 16.

If the dosing for a visit is +/- 7 days out of window, then the plasma concentration from that visit and all subsequent visits will be excluded from the PK summary. In addition, if the PK sampling date is >1 day after the dosing date, then the plasma concentration from that visit will be excluded from the PK summary.

All PK concentrations collected will be listed irrespective of the dosing or sampling occurring out of window.

9.2 Pharmacodynamics

Not applicable.

9.3 Immunogenicity

9.3.1 Autoantibodies

Not applicable.

9.3.2 Anti-bimekizumab antibodies

Anti-bimekizumab antibodies (ADAb) will be measured using a 3-tiered assay approach: screening assay, confirmatory assay, and titration assay. Samples confirmed as positive within the confirmatory assay will be further evaluated for the presence of neutralizing anti-bimekizumab antibodies specific to IL-17AA, IL-17FF or both. Samples will be taken at Baseline, then at study Weeks 4, 8, 12, 16, 20, 24, 36 and 48, and at PEOT and SFU timepoints.

ADAb samples are not analyzed when study participants are on a treatment other than bimekizumab. For study participants who switch from placebo to bimekizumab, samples are analyzed starting at the visit when the switch to bimekizumab occurs (Week 16). The sample at Week 16 will act as the Baseline for that treatment group.

The screening cut point will be used to determine the status of anti-bimekizumab antibodies in the test sample as Positive Screen (PS) or Negative Screen (NS). For samples presenting anti-bimekizumab antibody levels that are PS, a further confirmatory assay will be performed, and the result of which will be reported as either Positive Immunodepletion (PI) or Negative Immunodepletion (NI).

ADAb status for each sample will be derived as follows:

- Sample values that are either NS, or PS and NI and where the bimekizumab concentration is less than the validated ADAb assay drug tolerance limit will be defined as anti-bimekizumab antibody negative.
- Sample values that are either NS, or PS and NI and where the bimekizumab concentration exceeds the validated ADAb assay drug tolerance limit will be defined as inconclusive.

- Sample values that are PS and PI will be defined as ADAbs positive (regardless of availability of a titer value)
- Missing or non-evaluable samples will be defined as missing

Positive immunodepletion samples will be titrated, and the ADAbs titer (reciprocal dilution factor including minimum required dilution) will be reported. Subsequently, PI samples will also be subject to a neutralizing assay to evaluate the potential of ADAbs to neutralize the target binding of bimekizumab (IL-17AA or IL-17FF or both) in vitro.

Cumulative ADAbs status will be derived as follows:

The ADAbs status (positive, negative or missing) will be considered in a cumulative manner at each time point.

A study participant will be counted positive from the first visit at which the study participant achieved a positive ADAbs sample result to the end of the treatment period, regardless of any missing/inconclusive or negative ADAbs sample result.

If a study participant has only negative ADAbs samples or only one missing/inconclusive sample with all other ADAbs samples being negative, the study participant will be classified as negative. An exception remains for the Baseline Visit where only one sample could be available. If the sample is missing/inconclusive, then the sample will be classified as being negative for the cumulative ADAbs status.

Otherwise, the study participant will be classified in the missing ADAbs category.

Overall ADAbs status will be derived as follows:

A study participant will be classified as:

- Positive if the study participant has at least one positive sample up to the time point of interest (regardless of having missing/inconclusive data).
- Negative if the study participant has all the samples negative or only one missing/inconclusive sample with negative ADAbs samples up to the timepoint of interest.
- Missing if the study participant has more than one missing ADAbs result (or have more than one inconclusive sample) and all other available ADAbs samples are negative up to the time point of interest.

ADAbs categories will be derived as follows:

- **Pre ADAbs negative – treatment-emergent ADAbs negative (Category 1):** Includes study participants who are anti-bimekizumab antibody negative at Baseline and anti-bimekizumab antibody negative at all sampling points during the period of interest (one post-Baseline missing/inconclusive sample is allowed for subjects with pre- anti-bimekizumab antibody negative sample). This group also includes study participants who have a missing or inconclusive sample (either missing or inconclusive or insufficient volume) at Baseline (ie, pre-treatment) with all post-Baseline samples as ADAbs negative.
- **Pre ADAbs negative – treatment-emergent ADAbs positive (Category 2):** Includes study participants who are ADAbs negative at Baseline and ADAbs positive at any sampling points post-Baseline during the period of interest. This group also includes study participants who

have a missing sample (either missing or insufficient volume) at Baseline (ie, pre-treatment) with 1 or more post-Baseline samples as ADA_b positive.

- **Pre ADA_b positive – treatment-emergent reduced ADA_b (Category 3):** Includes study participants who are ADA_b positive at Baseline, and ADA_b negative at all sampling points post-Baseline during the period of interest.
- **Pre ADA_b positive – treatment-emergent unaffected ADA_b positive (Category 4):** Includes study participants who are ADA_b positive at Baseline and are ADA_b positive at any sampling point post-Baseline during the period of interest with titer values of the same magnitude as Baseline (ie, less than a predefined fold difference from the Baseline titer).
 - For this analysis, this is set at an increase of less than the validated Minimum Significant Ratio (MSR) of 2.07-fold from Baseline.
- **Pre ADA_b positive – treatment-emergent ADA_b boosted positive (Category 5):** Includes study participants who ADA_b positive at Baseline and are ADA_b positive at any sampling point post-Baseline during the period of interest with increased titer values compared to Baseline (equal to or greater than a predefined fold difference increase from Baseline titer which will be defined within the validation of the assay).
 - For this analysis, this is set at an increase equal to or greater than the validated MSR of 2.07-fold from Baseline.
 - Note: for any study participant who is ADA_b positive at Baseline and ADA_b positive at a post-Baseline time point during the period of interest, but for whom titers are not available to determine treatment unaffected or treatment boosted status, the study participant will be considered as treatment boosted, assuming no other samples are available.
- **ADA_b Inconclusive (Category 6):** Includes study participants who have an ADA_b positive Baseline (pre-treatment) sample and some post-Baseline samples during the period of interest are missing or inconclusive, while other post-Baseline samples are ADA_b negative.
- **Total treatment-emergent ADA_b positivity (Category 7 [Categories 2 and 5 combined]):** Includes study participants who are pre ADA_b negative – treatment-emergent ADA_b positive (Category 2) and pre ADA_b positive – treatment boosted ADA_b positive (Category 5).
- **Total prevalence of pre- ADA_b positivity (Category 8 [Categories 3, 4, 5 and 6 combined]):** Study participants that are tested ADA_b positive at Baseline.
- **Missing:** Includes study participants who are ADA_b negative, missing, or inconclusive at Baseline with some post-Baseline samples as missing or inconclusive, and other samples as ADA_b negative.

For purposes of efficacy subgroup analyses based on anti-bimekizumab antibody status, the following categories can also be used:

- ADA_b positive – This is defined as study participants who are anti-bimekizumab antibody positive on at least 2 time points while on treatment (ie, excluding Baseline, excluding SFU).
- ADA_b negative – Study participants for who either:

- All samples (including Baseline) are ADA_b negative and there are no missing or inconclusive samples
- Only 1 sample is ADA_b positive and all other samples (including Baseline) are ADA_b negative or missing or inconclusive
- Only 1 sample is missing or inconclusive and the remaining ADA_b samples are negative.
- ADA_b missing - Defined as study participants who do not fulfil the criteria for one of the 2 groups listed above.

The rationale for requiring at least 2 time points in which ADA_b levels are above the specified cut point is to exclude those study participants who have only one occurrence of ADA_b levels during the course of treatment. Including such study participants would increase the number of ADA_b positive study participants with potentially no impact on efficacy.

In the case that a sample is collected 1 or more days following the scheduled visit date in which the drug was administered, the ADA_b results for that sample will be associated with the scheduled visit and summarized accordingly. Such samples will also be considered when ADA_b results are summarized over a given study period.

Analysis

Immunogenicity will be assessed through summary tables and figures, and listing of individual results by participants. All analyses will be run on the AMS, unless specified otherwise.

- Summary of ADA_b status overall and by each visit separated by treatment group
- Summary of the time-point of the first occurrence of ADA_b positivity during the treatment period by treatment group. A plot of the titer by time to first ADA_b positivity will be prepared.
- All individual participant-level ADA_b results will be listed.
- The number and percentage of participants in each of the 8 ADA_b categories during the treatment period by treatment group.
- The prevalence of immunogenicity, separated by treatment group, and defined subcategory, will be reported by visit, defined as (cumulative) proportion of participants having confirmed positive ADA_b samples at any visit up to and including that visit. Missing samples will not be included in the denominator.
- The time to achieving treatment-emergent ADA_b positivity, separated by treatment group and defined subcategory, will be analyzed based on Kaplan-Meier methods. This will be shown only for Categories 2 and 8 above. Participants will be considered to have an event at the time point at which treatment emergent ADA_b positive is first achieved (taking the MSR into consideration for sub-category 5). Participants classified as treatment-emergent ADA_b negative will be censored at the time of the last available ADA_b result.
- A summary of HiSCR₅₀ responders at Week 16, separated by treatment group, as a function of ADA_b titer will be presented graphically.
- Individual plots of plasma bimekizumab concentrations/ ADA_b titer both plotted on the Y-axes by visit (x-axis) for the full treatment period (excluding SFU for interim analyses and

including SFU for final analyses) will be presented for participants with and without HiSCR₅₀ response at Week 16.

- Spaghetti plots of ADAb titer (y-axis) by visit (x-axis), separated by treatment group for all ADAb positive participants, including Baseline positive participants.
- Box plots of ADAb titer (logscale) by time to first ADAb positivity by treatment group.

The groups for defining ADAb status for safety subgroup analyses are as follows:

- AEs starting before first ADAb positive result
- AEs starting on or after first ADAb positive result
- AEs for participants who were always ADAb negative

This is further explained in Section 10.2.2.

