4.8 Examination of subgroups

Subgroup analyses will be performed on the HiSCR₅₀, HiSCR₇₅, and worst skin pain response endpoints by visit for the Initial Treatment Period and Maintenance Treatment Period. Additional subgroup analyses will be performed on the CFB in the worst skin pain score as measured by HSSDD and in the DLQI total score through Week 16 as described below.

Along with the tables described, there will be tables for HiSCR₅₀, HiSCR₇₅, and skin pain response endpoints which display the response difference and 95% CIs between each bimekizumab dose regimen versus placebo for each of the subgroups at Week 16. Corresponding forest plots will be prepared.

The following subgroup variables will be determined using Baseline data, except for analgesic use, lesion intervention, and antibody positivity:

- Age (<40 years, 40 to <65 years, \geq 65 years)
- Gender (male, female)
- Disease duration (<median, \geq median)

The median disease duration will be calculated based on all participants in the analysis set used for analysis.

- Region (North America [Canada, USA], Western Europe [Belgium, France, Germany, Italy, Norway, Spain, Switzerland, Denmark, Netherlands], Central/Eastern Europe [Greece], Asia/Australia [Australia, Israel, Turkey])
- Weight (\leq 100 kg, >100 kg)
- BMI (<25 kg/m², 25 to <30 kg/m², \geq 30 kg/m²)
- Race (Black or African American, White, All Other Races [American Indian or Alaska Native, Asian, Native Hawaiian or Other Pacific Islander, Other/Mixed])
- Systemic antibiotic therapy at randomization (yes, no)
- Prior biologic therapy for any indication (yes, no)
- Prior biologic therapy for HS (yes, no)
- Hurley Stage at Baseline (II or III)
- Analgesic users (yes, no), separately for the Initial Treatment Period and the Maintenance Treatment Period (Section 6.4.2 specifies how participants are classified as analgesic users)
- Lesion intervention (yes, no), separately for the Initial Treatment Period and the Maintenance Treatment Period

- Antibody positivity (confirmatory assay: negative or positive; see Section 9.3.2)
- Antihistamine users during the Initial Treatment Period (yes, no) (Section 6.4.2 specifies how participants are classified as antihistamine users) (applicable only to the skin pain response endpoint)

The following subgroups for analysis on the CFB in the worst skin pain score as measured by HSSDD and in the DLQI total score will be determined based on medication use during the Initial Treatment Period:

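### The antibody-negative efficacy subgroup accepts one positive sample with any number of others missing, yet with no positive sample it tolerates only one missing; some fully sampled participants are labelled missing

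*SAP*

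**What the plan says.** SAP Section 9.3.2 gives a three-way classification for the efficacy subgroup analyses.

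- **Positive:** the participant is "antibody positive on at least 2 time points while on treatment (ie, excluding Baseline, excluding SFU").
- **Negative:** there are three alternative routes. The first is that every sample is negative and none is missing or inconclusive. The second is "Only 1 sample is ADA_b positive and all other samples (including Baseline) are ADA_b negative or missing or inconclusive". The third is "Only 1 sample is missing or inconclusive and the remaining ADA_b samples are negative".
- **Missing:** "Defined as study participants who do not fulfil the criteria for one of the 2 groups listed above".

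The stated reason for requiring two positive time points is "to exclude those study participants who have only one occurrence of ADA_b levels during the course of treatment". The schedule in the same section is "Samples will be taken at Baseline, then at study Weeks 4, 8, 12, 16, 20, 24, 36 and 48, and at PEOT and SFU timepoints".

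Section 4.8 lists the subgroup as "Antibody positivity (confirmatory assay: negative or positive; see Section 9.3.2"). That is two levels, although the section it refers to defines three. Section 4.8 applies the subgroup to HiSCR50, HiSCR75 and skin pain response, with response differences and 95% CIs at Week 16 and forest plots.

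**The concern.** The two negative routes that allow incomplete data treat it in opposite ways. Where a positive has been seen, no amount of missing or inconclusive data prevents a negative label. Where no positive has been seen, two such samples are enough to prevent it. The participant with the stronger evidence of antibodies is the one more easily called negative.

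The definitions also count different samples. The positive definition leaves out Baseline and safety follow-up (SFU). The single-positive negative route includes Baseline and does not exclude SFU. Participants with two positives, only one of them on treatment, therefore fit neither definition, however complete their sampling.

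What is at stake is the content of the negative group. Under Section 4.2.1.1, stopping treatment for an adverse event (AE) or lack of efficacy is set to nonresponse. A participant with a single positive who stops for one of these reasons can then be counted as an antibody-negative nonresponder, which lowers that group's response rate.

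**Working it through.** No figure in the SAP bears on this point, so there is none to reproduce. The check applies the Section 9.3.2 rules to sample patterns for participants randomized to bimekizumab: Baseline plus 8 on-treatment samples (Weeks 4, 8, 12, 16, 20, 24, 36 and 48), 9 in all, with SFU added in one case.

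**1. Individual patterns**

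| Pattern | On-treatment positives | All positives | Missing or inconclusive | Class |
|---|---|---|---|---|
| Baseline negative, Week 4 positive, other 7 missing | 1 | 1 | 7 | negative |
| Baseline negative, Week 4 negative, other 7 missing | 0 | 0 | 7 | missing |
| 1 on-treatment positive, 6 negative, 2 missing | 1 | 1 | 2 | negative |
| 7 negative, 2 missing | 0 | 0 | 2 | missing |
| Baseline positive, 1 on-treatment positive, 7 negative | 1 | 2 | 0 | missing |
| Baseline negative, 1 on-treatment positive, 7 on-treatment negative, SFU positive | 1 | 2 | 0 | missing |

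Rows 1 and 2 differ only in the Week 4 result, and it is the positive participant who enters the negative group. Rows 3 and 4 show the same inversion with two missing samples. Rows 5 and 6 are labelled missing with nothing missing.

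**2. Exactly one positive.** There are 9 positions for the positive and 2 states (negative; missing or inconclusive) for each of the other 8 samples: 9 × 2^8 = 2,304 patterns. All are classed negative, with 0 to 8 samples missing or inconclusive. Only 9 + 72 = 81 of them have no more than one such sample.

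**3. Complete sampling, exactly two positives.** There are 9 × 8 / 2 = 36 patterns. Both positives are on treatment in 8 × 7 / 2 = 28, which are classed positive. The other 8 pair Baseline with one on-treatment visit and are classed missing. These are counts of patterns, not frequencies of participants.

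**4. The early dropout.** Take a participant who is positive at Week 4 and then stops. Section 3.2.2 assigns the premature end of treatment (PEOT) antibody sample to the next antibody visit, here Week 8, and treats it as observed there.

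- PEOT positive and counted as on treatment: two on-treatment positives, so positive.
- PEOT not positive, SFU positive and counted: two positives but only one on treatment, so missing.
- Neither positive: one positive, so negative.

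A participant who stops before Week 4 has at most one on-treatment sample (PEOT mapped to Week 4) and cannot be classed positive.

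**5. Size, on assumed values only.** Suppose 250 other participants in the negative group respond at 55% (137.5 expected responders) and d nonresponding single-positive dropouts join them. The group's rate is 137.5 / (250 + d):

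- d = 2: 54.6%
- d = 5: 53.9%
- d = 10: 52.9%
- d = 20: 50.9%

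The fall runs from 0.4 to 4.1 percentage points. Neither the 250, the 55% nor any value of d comes from the SAP.

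**The case against.** The strongest reply is that not calling a single positive antibody positive is a deliberate choice with a stated reason, and that little hangs on it. Section 9.3.2 offers these categories permissively, Section 4.8 limits subgroup summaries to descriptive statistics, and no confirmatory test uses them. Other outputs do not depend on the rule: HiSCR50 response at Week 16 by titer, individual concentration and titer plots by response, full listings, and an overall status for which one positive is enough.

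All of this stands and limits the weight of the point. It does not remove the inconsistency. The rationale supports treating a well-sampled, isolated positive as not positive. It does not address a single positive whose persistence could not be observed, and keeping someone out of the positive group does not require putting them in the negative group when a third group exists. Differing from the overall status is legitimate; labelling a fully observed participant missing is not.

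A reader might go further and infer that participants who become positive and stop early cannot be classed positive and fall into the negative group by default. The documents do not support that: as step 4 shows, a positive PEOT or SFU sample moves them elsewhere. Section 9.3.2 also does not say that visits after discontinuation count as missing samples. The inversion does not depend on that, because the section classes samples that are not confirmed positive as inconclusive when drug concentration exceeds the assay's tolerance limit, which can happen in participants still on treatment.

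**Conclusion.** The concern holds as an internal inconsistency in a stated rule. Read literally, Section 9.3.2 calls one positive with any number of missing or inconclusive samples negative, calls no positive with two such samples missing, and calls some fully sampled two-positive participants missing (8 of the 36 complete patterns over Baseline and Weeks 4 to 48, plus the SFU case). These classifications rest on the wording alone; the SFU case further assumes that SFU counts as a sample in the negative definition, which the text does not exclude.

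Contamination of the negative group by early-stopping, single-positive nonresponders is possible, but its size is unknown because the SAP gives no antibody incidence, dropout rate or response by antibody status. A reader might infer that the subgroup hides an antibody effect on efficacy. That is not established: the path needs no second positive at PEOT or SFU, the summaries are descriptive, and other planned displays would show the relation. No primary or secondary test is affected.

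**What to change.** In Section 9.3.2:

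- Allow a single positive in the negative group only if no more than one other sample is missing or inconclusive, matching the limit already set where there is no positive. Send single positives with more than that to the residual group.
- Rename the residual group indeterminate, since it can hold participants with complete sampling.
- State for each definition whether Baseline, on-treatment samples (including mapped PEOT) and SFU count.
- Assign Baseline positive plus one on-treatment positive explicitly, and not to the negative group. Restricting every definition to on-treatment samples would not do: it would make such a participant negative, including one with a boosted titer (Category 5). Assign one on-treatment positive plus a positive SFU sample explicitly as well.

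In Section 4.8, replace the two-level subgroup with the three levels and say how the third is displayed.

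The cost is SAP wording and one derivation, with no new data. Some participants move from negative to indeterminate, so the negative group is slightly smaller.
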